Endpoints	
 
• All-cause in-hospital mortality
 
• Morbidity at defined post-diagnosis intervals and over 7 consecutive days 
 
- Mean total SOFA score (age <math>\geq 16</math>)
 
- PELOD score (age <math>< 16</math>)
 
- <math>\Delta</math>SOFA or dPELOD score for day-to-day comparisons
 
 
 
• Extent and severity of Purpura lesions
 
• Need for reconstructive surgery (amputations, skin grafts)
 
• Length of ICU stay (days)
 
• Length of hospital stay (days)
 
• Changes in hematological parameters 
 
- WBC count
 
- Thrombocyte count
 
- Hemoglobin
 
 
 
• Changes in coagulation parameters 
 
- Prothrombin time (PT)
 
- Activated partial thromboplastin time (aPTT)
 
- Fibrinogen
 
- D-dimers
 
- Thrombin-antithrombin complex (TATc)
 
- Protein C activity
 
- Antithrombin III activity
 
 
 
• Changes in inflammatory parameters 
 
- C-reactive protein (CRP)
 
- Procalcitonin (PCT)
 
- Interleukin 6 (IL-6)
 
 
 
• Changes in organ dysfunction parameters 
 
- Glucose
 
- Lactate
 
- Creatine kinase (CK)
 
 
 
• Duration of mechanical ventilation (days)
 
• Duration of renal replacement therapy (days)
 
• Vasopressor use (days/doses)
 
• Sepsis-inducing pathogen
 
• Adverse event related to PF treatment (reporting as per decision of the investigator) 
 
- Bleeding
 
- Thrombotic events
 
 
 

Inclusion criteria	
 
- Diagnosis of severe sepsis and Purpura fulminans
 
- Signed informed consent (according to local legal regulations)
 

Exclusion criteria	
 
- premature neonates (<math>< 36</math> gestational week)
 

Centers	Approx. 30 participating centers in Germany, Austria, Ireland, UK, Italy, Spain, Netherlands (selected centers)

Timetable	First patient in	Q3 2015
	Registry duration	3 years, with an option of prolongation
	Estimated enrolment	Approx. 50 patients/year
	Interim Analysis	Biannually

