### **8.2. Setting**

The registry will include comprehensive records on diagnosis, morbidity and management of SAPF, supplied in the form of eCRFs by the participating centers over a period of three years.

The provision of informed consent by the patient or patient's legal guardian will be required for inclusion in accordance with local legal regulations.

The causal SAPF-inducing pathogen will be identified by microbiological examination.

The presence of Protein C deficiency and its contribution to the clinical manifestations of SAPF will be examined upon enrolment by determinations of Protein C concentration and activity, and subsequently documented in the eCRF. Changes in Protein C levels resulting from supplementation will be monitored as well.

The registry will also compare data on the efficacy of therapeutic approaches including or omitting Protein C supplementation.

A further aspect of specific interest is the stratification of outcomes by demographic (e.g. age, sex) and clinical criteria (e.g. morbidity at admission, causal pathogen), in order to identify subgroups of patients with above-average or marginal responsiveness to Protein C supplementation.

The contribution of supportive measures (e.g. assisted ventilation, renal replacement therapy, fluid resuscitation) and co-medication (e.g. vasopressors, corticosteroids, heparin etc.) will be evaluated as well.

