**Flowchart**

Activity / Endpoint	Baseline 	Post-diagnosis period (days)					End of study at hospital discharge or in-hospital death after ICU discharge
		1	3	5	7	ICU discharge or death on ICU after day 7	
Confirm inclusion criteria	x						
Provision of informed consent 	x						
Demographic data collection (incl. ethnic origin)	x						
Risk factors (vaccination status, asplenia) and comorbidities	x						
Estimated time of SAPF onset (hours)	x						
Mortality prediction (APACHE II/SAPS II  or PRISM III  score)	x						
Morbidity assessment (SOFA  /PELOD  score)	x	x	x	x	x		
Laboratory parameters (hematology, coagulation, inflammation)	x	x	x	x	x		
Purpura lesion assessment (c.f. eCRF)	x	x	x	x	x		
Vasopressor use record	x	x	x	x	x	x	
Site, source and origin of infection (including viral)							x
Concomitant causal, supportive and adjunctive treatment (c.f. eCRF)		x	x	x	x	x	
Cumulative dose of blood products and anti-coagulant treatment		x	x	x	x	x	
Antimicrobials		x	x	x	x	x	
Days in ICU							x
Days on mechanical ventilation							x
ECMO and circulatory support systems		x	x	x	x	x	
Days/type on renal replacement therapy							x
Purpura-related surgery (fasciotomy, debridement, amputation)							x
In-hospital mortality assessment		x	x	x	x	x	x
Days in hospital							x
Adverse drug reactions							x

 admission at ICU; according to local regulations APACHE II/SAPS II and SOFA scores will be used in patients aged above 16 PRISM III and PELOD scores will be used in patients aged below 16

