#### 8.4. Data sources

Registry subjects will be identified by the participating centers. The recruitment will be primarily based on the concomitant presence of clinical signs of sepsis and *Purpura fulminans*. Clarification of the underlying etiopathogenesis will be performed *post hoc*, upon collection of additional clinical and laboratory data.

Data capture comprises assessment at baseline and at several intervals of 24 (initially) and 48 (subsequently) hours for an overall period of 7 days, while in ICU. A final appraisal of the patient's status will take place at the time point of discharge from the hospital.

The exposure to individual therapeutic agents will be deduced from doses and frequency of application during the period spent in ICU.

The influence of potential confounding variables and effect modifiers (e.g. concomitant anticoagulant medication, fluid resuscitation, renal replacement therapy etc.) will be extrapolated from the corresponding specific entries in the eCRF.

The outcome indicators have been previously validated and are routinely used.

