## 8.7. Data analysis

A binary logistic regression model will be fitted for the all-cause in hospital mortality to compare the efficacy of the different treatments (e.g. with or without Protein C supplementation). To adjust for confounders, causal pathogen, baseline Apache II (PRISM III) score, laboratory parameters, age, sex, co-medication etc. can be included as covariates in this model.

Consecutive changes in SOFA or PELOD scores ( $\Delta$ SOFA, dPELOD) at individual post-diagnosis intervals and their mean values calculated for the observation period of 7 days will be compared to the scores determined on admission (baseline). Changes in these organ failure indices will be examined by means of

- Paired samples T-test
- Linear model with morbidity score baseline adjustment and alternative co-variables (e.g. hematological, coagulation or inflammatory parameters)

Explorative analysis without correction and with a pre-set level of significance of 0.05 will be conducted as well.

All endpoints will be subjected to descriptive statistical analysis with determination of 95-percent confidence intervals. Between-group comparisons will be preceded by distribution analysis (Shapiro-Wilk Test of normality). Depending on the data distribution, *post hoc* processing will involve either parametric (one-way ANOVA, T test) or non-parametric (Kruskal-Wallis, Mann-Whitney U-test) approaches.

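### Renal replacement therapy (and, less explicitly, vasopressors and ventilation) may serve both as outcome and as adjustment variable, with no rule limiting adjustment to values before Protein C start

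*Combined protocol and SAP*

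**What the plan says.** Organ support appears in several roles.

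- **Endpoint.** The Abstract lists "Duration of renal replacement therapy (days"), "Duration of mechanical ventilation (days") and "Vasopressor use (days/doses").
- **Treatment to be evaluated.** Section 8.2 announces an assessment of "The contribution of supportive measures (e.g. assisted ventilation, renal replacement therapy, fluid resuscitation") and, in the same sentence, "co-medication (e.g. vasopressors, corticosteroids, heparin etc.) will be evaluated as well".
- **Confounder or effect modifier.** Section 8.4 refers to "The influence of potential confounding variables and effect modifiers (e.g. concomitant anticoagulant medication, fluid resuscitation, renal replacement therapy etc"), to be derived from eCRF entries.
- **Covariate in the mortality model.** Section 8.7 fits a logistic regression for in-hospital death and adds that "laboratory parameters, age, sex, co-medication etc. can be included as covariates in this model".

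The flowchart in section 8.2 fixes the timing. The row "Days/type on renal replacement therapy" and the row for ventilation days are marked only in the last column, at hospital discharge or death. The row for causal, supportive and adjunctive treatment starts on day 1. Vasopressor use is recorded at baseline (ICU admission), on days 1, 3, 5 and 7, and at ICU discharge or death. Section 8.4 derives drug exposure from doses and frequency over the ICU stay. No section defines a start time for Protein C or a reference time for patients who do not receive it.

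**The concern.** Section 6 describes multiple organ dysfunction as part of the disease. Organ support begun after diagnosis therefore reflects how the disease develops, and may reflect how well treatment works. If Protein C acts partly by preventing organ failure, a model that conditions on later RRT blocks part of the effect it is meant to measure. If unmeasured severity drives both RRT and death, conditioning on RRT also opens a non-causal path between Protein C and death.

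The planned evaluation of supportive measures has a separate weakness. Patients receive RRT because they are sicker, and they stop accumulating RRT days when they die. A comparison by ever/never use or by day totals can show an effect where there is none. Under section 11, registry results feed treatment recommendations sent to centers and outside parties, so both errors could reach practice.

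**Working it through.** **Step 1: roles and timing side by side.**

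| Measure | Endpoint (Abstract) | To be evaluated (8.2) | Adjustment role (8.4, 8.7) | Own flowchart row |
|---|---|---|---|---|
| RRT | days | named | named in 8.4; not named in 8.7 | last column only |
| Ventilation | days | named | not named; only through open-ended lists | last column only |
| Vasopressors | days/doses | named, as co-medication | 8.7 allows co-medication | baseline, days 1, 3, 5, 7, ICU discharge or death |

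Only RRT is explicitly in all three roles. On the flowchart, the RRT value available for adjustment is an end-of-study total or, at best, an entry from day 1 onward.

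**Step 2: the plan's own figure.** There is none to reproduce: the protocol states no effect size or power. The numbers below rest on assumed parameters and show direction and range only.

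**Step 3: Protein C odds ratio with and without post-baseline RRT.** Logistic simulation, 400,000 patients. S is measured baseline severity and U is unmeasured severity, both standard normal.

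- P(Protein C) = expit(0.5·S)
- P(RRT) = expit(a·ProteinC + 0.7·S + u·U)
- P(death) = expit(−0.5 + d·ProteinC + 1.0·RRT + 0.7·S + u·U)

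| a (Protein C → RRT) | d (direct) | u | OR adjusted for S | OR adjusted for S and RRT |
|---|---|---|---|---|
| −0.5 | −0.4 | 0 | 0.609 | 0.672 |
| −1.0 | −0.4 | 0 | 0.549 | 0.674 |
| −0.5 | −0.4 | 1 | 0.681 | 0.764 |
| −1.0 | −0.4 | 1 | 0.623 | 0.818 |
| −0.5 | 0 | 0 | 0.902 | 1.009 |
| −1.0 | 0 | 0 | 0.802 | 0.996 |
| −0.5 | 0 | 1 | 0.916 | 1.074 |
| −1.0 | 0 | 1 | 0.843 | 1.146 |
| 0 | −0.4 | 0 | 0.682 | 0.669 |
| 0 | −0.4 | 1 | 0.741 | 0.708 |

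Share of the log odds ratio lost = 1 − ln(OR with RRT)/ln(OR without RRT).

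- Row 1: 1 − 0.397/0.496 = 20%.
- Row 2: 1 − 0.395/0.600 = 34%.
- Row 3: 1 − 0.269/0.384 = 30%.
- Row 4: 1 − 0.201/0.473 = 58%.

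In rows 5 and 6 the whole effect runs through RRT and disappears. In rows 7 and 8 the sign reverses. In the last two rows Protein C does not change RRT use and nothing is lost; the small move away from 1 is what an odds ratio does when another predictor of death is added.

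**Step 4: estimated effect of organ support itself.**

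- *Ever/never use.* In step 3 the true RRT odds ratio is e^1.0 = 2.72. With u = 0 the model returns 2.67 to 2.73; with u = 1 it returns 4.78 to 4.83. The excess is confounding by indication.
- *Day totals.* Suppose RRT has no effect. Let time to death be exponential with mean 40 days over a 28-day stay, so mortality is 1 − e^(−28/40) = 50%. Let planned RRT last 1 to 14 days (uniform), cut short by death. With 40%, 60% and 100% of patients on RRT, the odds ratio per day is 0.961, 0.951 and 0.892. Per 7 days, 0.961^7 = 0.76 and 0.892^7 = 0.45. Ever/never use in the first two settings gives 0.991 and 0.995, close to the truth, because RRT is unrelated to severity there.
- *Day totals when organ failure drives both RRT and death.* Still with no RRT effect and mortality about 52%, the odds ratio per 7 days ran from 0.36 to 1.35, depending on the assumed time to death and RRT duration. The direction is not fixed.

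**The case against.** The case against is substantial, and much of it stands.

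- A reader might infer that all three organ-support measures are declared confounders. The text does not say so. Ventilation is never named as one, vasopressors enter only as co-medication, section 8.4 speaks of potential confounders, and the covariates in section 8.7 are optional. That limits the point but is no safeguard, since nothing rules the adjustment out.
- A reader might infer that a variable cannot be both endpoint and confounder. That is wrong. RRT already running before Protein C starts can genuinely confound mortality, while RRT duration afterwards is an outcome. The defect is the missing timing rule. Barring RRT altogether, or allowing only status at ICU admission, could add bias. In an illustration with a true Protein C odds ratio of 0.67, where RRT starts before Protein C and predicts both its use and death, omitting RRT gave 0.78 to 0.83 and including it gave 0.67.
- A reader might infer that ever/never coding always shows harm and day coding always shows benefit. Step 4 shows that neither holds in general.
- The eCRF is not among the documents. The supportive-treatment row refers to it and covers days 1, 3, 5 and 7, so dated RRT information may exist. If so, the repair is easier, but the plan would still need to say which value is used.
- Section 8.7 specifies no effect model for supportive measures, so the codings in step 4 are possibilities and not the declared analysis. Section 8.9 concedes that combined therapy may obscure the effect of one agent, but it does not address adjustment for events after treatment.

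**Conclusion.** The concern holds as a problem of roles and timing. Section 8.4 names RRT as a potential confounder, although its own flowchart row holds only a total that Protein C may affect and that death cuts short. No section confines adjustment to values before Protein C start.

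Adjusting for later organ support can bias the Protein C comparison. The shift is usually toward no effect if Protein C reduces organ failure: 20% to 58% of the log odds ratio in rows 1 to 4, and all of it in rows 5 and 6. It can go past no effect if unmeasured severity drives both organ support and death (0.84 to 1.15), and it is slight if Protein C does not affect organ support. The documents therefore do not support the stronger reading that such adjustment removes part of any Protein C effect. Every size rests on assumed parameters.

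Estimates of the effect of organ support itself are open to confounding by indication (ever/never use) or distorted by truncation at death (day totals), with direction and size depending on assumptions. The plan should be changed on both counts.

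**What to change.** 1. In sections 8.4 and 8.7, state that RRT, ventilation and vasopressors enter the Protein C models only as status at or before Protein C start. Define a comparable reference time for patients who do not receive Protein C. State that day totals and later use are never adjustment variables.
2. Use the baseline vasopressor record already scheduled. For RRT and ventilation, add a start date or a baseline yes/no item if the eCRF lacks one. A start date is preferable, because an admission item misses support begun between admission and Protein C start. If neither can be obtained, leave these two measures out of the adjustment set and name the residual confounding as a limitation in section 8.9.
3. Keep organ support after that time as outcomes only.
4. In section 8.2, replace the evaluation of the contribution of organ-support measures by a description of their use by group, with no effect estimate from ever/never use or day totals.

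The cost is protocol wording, possibly one or two eCRF items, and giving up effect claims for organ support.

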#### 8.5. Study size

Earlier reports on the incidence of SAPF [Darmstadt, 1998; Nicolas and Debonne, 2002] were based on the association of the condition with meningococcal sepsis. Conceivably, these data hardly permit extrapolation to the contemporary situation, which has substantially changed after the introduction of meningococcal vaccination [Maat et al., 2007]. Depending on the number of participating centers, a realistic forecast envisages the recruitment of 50 to 70 adult and pediatric patients during the first year of the registry, with subsequent possible increase to 100 per year. In view of the spread of meningococcal vaccination among children and adolescents, the expected proportion of adult patients might eventually exceed 50 %.

With regard to the relatively limited projected study size, and with regard to the lack of a uniform treatment concept for SAPF, demonstration of differences between individual treatment paradigms might require dichotomization (e.g. use vs. omission of Protein C supplementation) and could be applicable only to selected endpoints.

#### 8.6. Data management

Individual data will be collected in accordance with the flowchart by means of electronic Case Report Forms (eCRF) and transmitted by remote data entry to the server of the Center for Clinical Studies of the Jena University Hospital. The local user authentication is ensured by password-protected logins. A role-based hierarchical security structure warrants multi-tier prevention of unauthorized access. The communication between the participating site's workstation and the server is encrypted. Data processing employs the software OpenClinica, which fulfills the regulatory requirements (GCP, 21 CFR Part 1).

Data management will resort to electronic applications. The anonymity of data is warranted in the course of evaluation. A first plausibility check will take place during raw data input in the eCRF at the investigator site, with missing or implausibly aberrant values signaling imminent correction requirement. A further verification of plausibility and consistency will be conducted by applying a controversy-detection algorithm. Permission for data corrections will be conferred to a restricted number of authorized study personnel (e.g. site investigator, study nurse, data manager). A final plausibility check will take place upon receipt of the reply to queries and the eCRFs bearing all annotated modifications.

falsch

## 8.7. Data analysis

A binary logistic regression model will be fitted for the all-cause in hospital mortality to compare the efficacy of the different treatments (e.g. with or without Protein C supplementation). To adjust for confounders, causal pathogen, baseline Apache II (PRISM III) score, laboratory parameters, age, sex, co-medication etc. can be included as covariates in this model.

Consecutive changes in SOFA or PELOD scores ( $\Delta$ SOFA, dPELOD) at individual post-diagnosis intervals and their mean values calculated for the observation period of 7 days will be compared to the scores determined on admission (baseline). Changes in these organ failure indices will be examined by means of

- Paired samples T-test
- Linear model with morbidity score baseline adjustment and alternative co-variables (e.g. hematological, coagulation or inflammatory parameters)

Explorative analysis without correction and with a pre-set level of significance of 0.05 will be conducted as well.

All endpoints will be subjected to descriptive statistical analysis with determination of 95-percent confidence intervals. Between-group comparisons will be preceded by distribution analysis (Shapiro-Wilk Test of normality). Depending on the data distribution, *post hoc* processing will involve either parametric (one-way ANOVA, T test) or non-parametric (Kruskal-Wallis, Mann-Whitney U-test) approaches.

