## 9. Protection of human subjects

The Registry protocol is subject to approval by the IRB of the Friedrich Schiller University, Jena, which will serve as the supervisory ethic institution in charge. Approval of the Registry protocol by the responsible regional or national authorities will be sought after by participating centers which are outside of the jurisdiction of the IRB in charge.

Eligibility for an individual treatment modality will be defined by the responsible physician by fulfillment of the criterion "manifest clinical signs of sepsis-associated *Purpura fulminans*". The probability of inclusion into the Registry will not influence the physician's decision on the use of a selected medication.

An informed consent, signed by the patient or his/her legal representative, also comprising collection and use of medical data, will be sought for before enrolment into the Registry. However, in view of the rarity of the disease and the high mortality, usage of deviant regional and national regulations will be considered where appropriate and legally acceptable.

The protection of participant's privacy will be warranted by **a)** pseudonymization of patient personal data at the participating center for the duration of the clinical observation period, **b)** data transmission using a secure password-protected login and **c)** ultimate anonymization of the collected information upon verification of data consistency and plausibility. The pseudonymous ID list will

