assign a four-digit-number to each participant and contain a pre-defined minimum of personal information considered essential for the processing of queries pertaining to accuracy, plausibility and consistency. For the communication with the Data Management, only the assigned four-digit-numbers will be used. The identity a patient can be disclosed only to the authorized study team members at the participating sites. Personal identity data (i.e. the pseudonymous ID record) are subject to transformation upon confirmation of the completeness of relevant information by the Registry Data Management. Numbers assigned in the process of pseudonymization will be replaced by the Data Management, in order to abrogate the possibility of tracking back patient's identity, while retaining the possibility to allocate data to the center of origin. The primary ID lists at the participating sites will be stored for at least 10 years in a mode, which precludes access of non-authorized persons. Compliance with this requirement will be verified in the course of monitoring site visits.

The sovereignty over the Registry data is exerted by the Advisory Committee. Documentation will take place at the Center for Clinical Studies of the Jena University Hospital. Registry data will be processed automatically, with scheduled regular backups. Registry data are accessible to a limited number of staff members, who are directly involved in this project. Data media are stored in a secured space on the premises of the Center for Clinical Studies, with access permitted only to the system administrator.

Publication of Registry data will occur only in aggregated form, without disclosure of details of subjects and participating investigation sites. These conditions also apply to the dissemination of Registry data, e.g. on request of external investigators. In the latter case an approval of the IRB will be solicited.

The regulations pertaining to patients' welfare and privacy protection comply with the international and national norms and legislation (Helsinki Declaration, GCP, GEP national regulations of participating countries).

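### The Protein C comparisons in section 8.7 do not provide for centre; if use and mortality both vary by centre, standard errors will be too small and centre may confound

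*Combined protocol and SAP*

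**What the plan says.** Section 8.7 (Data analysis) gives the mortality analysis in one sentence: "A binary logistic regression model will be fitted for the all-cause in hospital mortality", with use or non-use of Protein C as the example contrast. Adjustment is optional and the list is open-ended. After pathogen, baseline severity score and laboratory parameters it ends: "age, sex, co-medication etc. can be included as covariates in this model". Neither centre nor country is named. For other endpoints the section plans t-tests, ANOVA, rank tests and a linear model for the organ failure scores. It mentions no random effect, generalised estimating equation or clustered variance, nor does any other section. Section 8.1 promises only suitable statistical techniques.

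The setting is multicentre. The Abstract lists "Approx. 30 participating centers in Germany, Austria, Ireland, UK, Italy, Spain, Netherlands (selected centers"). It plans "Approx. 50 patients/year" for "3 years, with an option of prolongation". Section 8.5 forecasts "recruitment of 50 to 70 adult and pediatric patients during the first year of the registry, with subsequent possible increase to 100 per year", and acknowledges that the condition has no uniform treatment concept. On who decides treatment, section 9 says: "Eligibility for an individual treatment modality will be defined by the responsible physician". The same section says that patient numbers are replaced at anonymisation "while retaining the possibility to allocate data to the center of origin". Section 11 promises each centre a twice-yearly comparison of its performance with the average of all participants.

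**The concern.** Section 8.1 gives the Protein C comparison special emphasis. Under section 7 it feeds recommendations on Protein C use, which section 11 has updated after each biannual evaluation. A spurious result would therefore reach treating centres.

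Two separate problems can arise when patients are nested in centres.

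- **Precision.** If some centres use Protein C more than others, and mortality also differs by centre, patients from one centre carry overlapping information about the contrast. A single-level model counts them as independent and gives standard errors that are too small.
- **Confounding.** If centres that use more Protein C also have better or worse outcomes for other reasons, that difference appears in the Protein C odds ratio. Widening the interval does not correct this.

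The plan makes both plausible: many centres, seven countries, no shared treatment approach, and local decisions. It also intends to compare performance between centres.

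**Working it through.** The plan states no power, effect size or ICC, so there is no figure to reproduce. The check asks how far the actual error of a nominal 5% test could move.

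**Inputs from the documents**
- Centres: about 30 (Abstract).
- Patients, lower case: 50 × 3 = 150, or 150/30 = 5 per centre (Abstract).
- Patients, upper case: 70 + 100 + 100 = 270, or 270/30 = 9 per centre (section 8.5, which calls the rise to 100 a year only possible).
- Mortality: 50% used; section 6 says above 50%.
- Level: 0.05 (section 8.7, stated for the explorative analysis), taken as two-sided.

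**Assumed, not in the documents:** the outcome ICC, how strongly Protein C use clusters by centre, and the spread of centre sizes.

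**1. Approximation.** With m patients per centre and CV the coefficient of variation of centre size:

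DE = 1 + ((1 + CV²)m − 1) × ICC(outcome) × ICC(treatment)

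Actual error = 2 × (1 − Φ(1.96/√DE)), and the correct interval is √DE times as wide.

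With m = 5, CV = 0 and outcome ICC 0.10:
- Use unrelated to centre, ICC(treatment) = 0: DE = 1.00, error 5.0%. This holds at any outcome ICC.
- Use half clustered, 0.5: DE = 1 + 4 × 0.10 × 0.5 = 1.20, width × 1.10, error 7.4%.
- Use fully set by centre, 1: DE = 1 + 4 × 0.10 = 1.40, width × 1.18, error 9.8%.

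The product of the two ICCs carries the argument: both must be above zero.

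**2. Simulation under no treatment effect.** 30 centres, unadjusted logistic Wald test, 2,500 runs per setting (Monte Carlo standard error about 0.4 points at 5%, up to 0.9 at 27%). Cells give type I error in % at latent-scale ICC 0.05 / 0.10 / 0.20.

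| Protein C use | N=150, equal centres | N=150, unequal | N=270, equal | N=270, unequal |
|---|---|---|---|---|
| Unrelated to centre | 5.0 / 4.7 / 4.6 | 5.1 / 5.3 / 4.6 | 4.5 / 5.2 / 5.1 | 5.6 / 5.1 / 5.0 |
| Partly centre-driven (SD 1.5 on logit scale) | 5.6 / 5.7 / 7.0 | 6.0 / 7.4 / 10.2 | 5.5 / 7.4 / 8.7 | 7.8 / 8.3 / 12.2 |
| Wholly set by centre | 6.3 / 8.0 / 12.6 | 8.6 / 13.4 / 20.2 | 8.2 / 11.6 / 19.0 | 12.8 / 18.8 / 27.4 |

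Two further simulations with unequal centres agree in order of magnitude.
- 2,000 runs: partly centre-driven use gave 6-10% (mean 5 per centre) and 7-13% (mean 9); use wholly set by centre gave 7.5 / 10 / 17% and 10 / 16 / 27%.
- 500 runs (Monte Carlo error 1 to 2 points): partly centre-driven use gave 6 / 8 / 9% and 5 / 7 / 12%; use wholly set by centre gave 8 / 13 / 21% and 12 / 19 / 32%.

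The approximation uses an observed-scale ICC and the simulations a latent-scale one, so their figures should not be matched at the same nominal ICC.

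**3. Remedies.**
- Cluster-robust errors (t, 29 df): 4.2-5.7% with equal centres, but 5.6-9.8% with strongly unequal ones. No small-sample-corrected version was simulated.
- Random intercept (likelihood ratio test, unequal centres, 500 runs): 6 / 6 / 7% at N=150 and 7 / 6 / 6% at N=270 with use set by centre; 3-6% with partly centre-driven use.

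**4. Confounding.** Assume a correlation of 0.5 between lower centre mortality and more Protein C use, ICC 0.10 and partial clustering. The ordinary model then shows a spurious log odds ratio of about −0.27 (odds ratio exp(−0.27) ≈ 0.76) and rejects in 18-21% of runs. Cluster-robust errors leave about 15%, and the random intercept about 10%.

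**The case against.** A reader might infer that the intervals are certain to be too narrow and false positives too frequent. The documents do not support that. Section 9 describes a decision by the responsible physician, not a centre policy. No section says that Protein C use or mortality differs by centre, and no ICC is given. If use is unrelated to centre, the ordinary model keeps its level. The largest error rates need use wholly set by centre, and those at 9 per centre also need the optional rise in recruitment.

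A reader might also infer that centre has been ruled out as a covariate. It has not: the list is optional and open-ended, so centre is unspecified rather than excluded.

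Two further arguments have weight. Pathogen and severity score, if included, could absorb some between-centre variation; the tabulated simulation was unadjusted. And the registry has no formal power calculation or confirmatory alpha, while section 8.5 concedes that treatment comparisons will be limited, so a type I error argument counts for less than in a confirmatory trial.

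All of this limits the size of the concern and makes it conditional. It does not remove the omission. The sponsor cannot know in advance that use is unrelated to centre, and an open covariate list leaves the choice until results have been seen. The confounding argument does not depend on a formal alpha.

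**Conclusion.** The point holds in conditional form. Section 8.7 makes no provision for centre in the registry's most emphasised comparison, although the data would allow it. Harm to the standard errors requires both Protein C use and mortality to vary by centre; confounding requires the two to be associated across centres.

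Across the simulations, for a latent ICC of 0.05 to 0.20, the type I error of a nominal 5% test is:
- near 5% if use does not cluster by centre;
- about 6-10% at 5 patients per centre and 5-13% at 9, if use is partly centre-driven;
- about 6-21% and 8-32% respectively, if use is wholly set by centre, which is an extreme case.

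These ranges rest on assumed ICCs, degrees of clustering and centre sizes. Confidence is high on the omission and moderate on its size.

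**What to change.** Add to section 8.7 that the mortality model, and the models used for other between-group comparisons, include a random intercept for centre, with the ordinary model reported as a sensitivity analysis. Rank tests take no random intercept and can stay as unadjusted description. Add a table of Protein C use and mortality by centre, so that readers can see whether either clusters.

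Name cluster-robust errors with a small-sample correction as a fallback for the standard errors only. They leave the estimate unchanged and so do nothing about confounding by centre. The random intercept reduces that confounding but does not remove it, and the report should say so. Thirty fixed centre effects are not advisable: with about 5 patients each they would be unstable.

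The cost is a short addition to section 8.7, a little more analysis work and somewhat wider intervals. No new data are needed, because the centre of origin is retained.
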